### 20.3 Participant Population for Analysis:

For Aim 1, we will include all participants who complete the at-home BinaxNOW test within 72 hours (N=358) and have nasal PCR results. For Aim2, we will include all participants who have both nasal and lollipop PCR results.

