## 1.0 Study Summary

Study Title	Safe and Healthy Schools
Brief Summary	This study will target Madison Metropolitan School District school children ages 4-19 and staff who have not had a previous positive COVID-19 test within the past 3 months. It will enroll children and adults for 1-3 days to explore whether serial “at-home” BinaxNOW testing is feasible and non-inferior to “at school” single PCR testing for the evaluation of symptomatic individuals with a negative initial BinaxNOW. It will also explore whether lollipop swabs are more acceptable and perform as well as nasal swabs with PCR testing.
Number of study sites	1
Study Design	Community-based empirical research
Primary Objective	(1) Determine whether “at-home” BinaxNOW testing is feasible for families, (2) Evaluate whether serial “at-home” BinaxNOW testing is non-inferior to “at school” single PCR testing, (3) Compare the acceptability of lollipop swabs and nasal swabs, and (4) Compare the performance of lollipop swabs to nasal swabs with PCR-based testing.
Secondary Objective(s)	NA
Research Intervention(s)/ Investigational Agent(s)	NA
Drugs/devices used on study (including any IND/IDE #)	This study will evaluate the BinaxNOW COVID-19 Ag Card and the “lollipop” swab sample collection method
Study Population	Madison Metropolitan School District school children ages 4-19 and staff
Sample Size	400 with negative at-school BinaxNOW and 50 with positive at-school BinaxNOW. Total n=450.
Study Duration for individual participants	Up to 5 days
Study Specific Abbreviations/ Definitions	PCR: polymerase chain reaction EUA: emergency use authorization

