## PROTOCOL TITLE: SAFE AND HEALTHY SCHOOLS

1. Is ‘at-home’ BinaxNOW testing feasible for families?
2. Is serial ‘at-home’ BinaxNOW testing non-inferior to ‘at-school’ single PCR testing?

**Aim 2:** We will test the hypothesis that lollipop swabs are more acceptable to individuals and PCR testing is non-inferior to performing PCR on nasal swabs. To test this hypothesis, we will work with MMSD schools to incorporate a lollipop swab for PCR at the time a symptomatic student or staff receives a nasal swab for PCR that is part of the DHS program. We will address the following two key questions:

1. Are lollipop swabs more acceptable to individuals when compared to nasal swabs?
2. Will lollipop swabs perform as well as nasal swabs with PCR-based testing?

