### 3.2 Hypotheses to be tested:

**Aim 1.1:** “At-home” BinaxNOW testing will be feasible for families.

**Aim 1.2:** Serial “at-home” BinaxNOW testing is non-inferior to “at school” single PCR testing.

**Aim 2.1:** Lollipop swabs are more acceptable to individuals than nasal swabs.

**Aim 2.2:** Lollipop swabs will perform as well as nasal swabs with PCR-based testing.

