### 5.3 Criteria that define who will be excluded from the final study sample:

If certain samples do not provide a result—such as if samples are missing, compromised, or invalid—the subject will not be included in analyses for one or both of the study aims. Criteria for exclusion from analyses are as follows:

Aim 1

-Missing nasal PCR result

-Do not successfully complete an at-home BinaxNOW test within 72 hours of the at-school BinaxNOW test

Aim 2

-Missing nasal PCR result

-Missing lollipop PCR result

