## PROTOCOL TITLE: SAFE AND HEALTHY SCHOOLS

the client's backup routine. If files are accidentally backed up, they will be manually removed from the backup and deleted permanently from all locations except REDCap. Additionally, the SMPH VPN via the Palo Alto Global Protect client, configured and available for use on all DOP endpoints, will be enabled and connected by the end-user on data collection endpoints whenever study data is being accessed or transferred.

The study team will make every effort to enter data directly into REDCap in real time. The study team will use a wireless hotspot for reliable internet connectivity, rather than relying solely on the school's Wi-Fi connection, to minimize the need for this emergency data collection protocol.

After this basic information is collected, the study coordinator will begin testing. If the participant did not already receive an at-school BinaxNOW test, then the study coordinator will collect the nasal swab for and administer the BinaxNOW test. When study staff collect the nasal swab for the BinaxNOW test, they may encourage parents/legal guardians to comfort their child. Participants under the age of 18 will only receive nasal swabs when their parent or legal guardian is physically present. If a potential participant is unwilling to have the study team collect a nasal swab, they will not be enrolled in the study.

Next, the study coordinator will guide the participant through completing a "lollipop" swab at school. The lollipop swab is obtained by having the participant suck on a swab for 20 seconds in the same way that they would suck on a lollipop. The study coordinator will ask whether they prefer the PCR nasal swab or lollipop collection method. The study coordinator will provide the lollipop swab to Exact Sciences or ACL for analysis. For Exact Sciences, it will be labeled with the study ID and date of collection. For ACL, lollipop samples will have a label and accompanying requisition form that will both contain the subject's full name, date of birth, and the date and time of collection.

If the study team does not have any BinaxNOW tests due to a supply shortage, study participation will end after the lollipop swab is collected. If BinaxNOW tests are available and the participant intends to do the at-home antigen testing, then the at-school antigen testing is required.

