### 20.4 Statistical Methods:

**Aim 1.** Sensitivity, specificity, positive predictive value (PPV) and NPV of the proposed BinaxNOW testing procedure for symptomatic subjects will be calculated and reported along with the corresponding two-sided 95% confidence interval. Formal non-inferiority testing of the BinaxNOW testing procedure with PCR will be conducted with respect to sensitivity and specificity with a non-inferiority margin of  $\delta=5\%$  and a sensitivity/specificity of PCR of 99%.

**Aim 2.** Results obtained from nasal and lollipop swab-based PCR testing will be summarized in tabular format. Concordance between the PCR test results will be evaluated by calculating the Kappa statistic which will be reported along with corresponding two-sided 95% confidence interval. The nonparametric bootstrap technique will be used to construct the confidence interval. A kappa statistic of  $>0.95$  will be considered as sufficient to define lollipop swab test non-inferior to the gold-standard PCR testing of nasal swabs. Furthermore, standard diagnostic test outcomes, i.e., sensitivity, specificity, NPV and PPV will be calculated (using the nasal swab-based

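### Primary objective 3 (swab acceptability) has no planned analysis, and the only Aim 2 population requires two PCR results that have no bearing on a stated preference

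*Combined protocol and SAP*

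**What the plan says.** Section 1.0 lists as a primary objective: "Compare the acceptability of lollipop swabs and nasal swabs". Section 3.2 turns this into a directional hypothesis, Aim 2.1: "Lollipop swabs are more acceptable to individuals than nasal swabs". Aim 2.2, on PCR performance, sits under the same aim.

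The one acceptability measure described in the procedures is in section 13.3, at the lollipop step: "The study coordinator will ask whether they prefer the PCR nasal swab or lollipop collection method". Section 13.4 also lists opinion questions on collection methods, without giving their wording.

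The population is set for Aim 2 as a whole. Section 20.3 says: "For Aim2, we will include all participants who have both nasal and lollipop PCR results". Section 5.3 excludes from Aim 2 anyone without a nasal PCR result and anyone with "Missing lollipop PCR result". Section 5.2 is looser and asks only for a lollipop swab that the laboratory could result. None of these sections gives Aim 2.1 a population of its own.

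The Aim 2 hypothesis in section 20.1 concerns test performance only. The Aim 2 methods in section 20.4 begin "Results obtained from nasal and lollipop swab-based PCR testing will be summarized in tabular format" and go on to kappa, sensitivity, specificity, predictive values and non-inferiority. The preference answer does not appear. Section 20.6 rules out imputation and has no rule specific to acceptability.

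**The concern.** Two things are wrong, and they compound each other.

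First, a primary superiority hypothesis has nothing in the plan that could decide it. The measure, the denominator, the handling of people with no preference and the threshold for calling the lollipop more acceptable would all be chosen after the data are seen.

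Second, the only population offered for that choice is the wrong one. Whether a laboratory returned a result says nothing about which swab a person preferred. The rule removes two different groups:

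- People whose sample was lost, invalid or not matched to a record. Their answers are valid and are wasted.
- People who could not give a usable sample with one of the swabs. Their failure may itself be evidence on acceptability, so removing them conditions the comparison on both swabs having worked.

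At stake is whether the reported share preferring the lollipop describes the people who were asked, or only those for whom both methods succeeded.

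**Working it through.** **Plan's own figure.** There is none for acceptability. The only powered figure in section 20 is N = 358 for the Aim 1 negative predictive value (91% against 95%, one-sided 0.05, 90% power). It reproduces: an exact binomial test on 358, with success at 335 or more true negatives, has size 0.0487 and power 0.909. It does not bear on Aim 2.1.

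**Text check.** Set side by side:

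| Element | Aim 2.1 acceptability | Aim 2.2 PCR performance |
|---|---|---|
| Hypothesis in 3.2 | yes | yes |
| Hypothesis in 20.1 | none | non-inferiority |
| Method in 20.4 | none | kappa, accuracy, non-inferiority |
| Population in 5.3 and 20.3 | none of its own | both PCR results |
| Data needed | an answer given at school | two laboratory results |

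**Illustration of size.** The documents give no preference rate and no swab-failure rate, so all inputs except 450 (section 1.0) are assumptions.

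- True share preferring the lollipop among all 450 asked: 0.50.
- Share lost to the both-results rule: r = 2%, 5%, 10%.
- Share preferring the lollipop among those lost: q.
- Share inside the 20.3 set: p = (0.50 − q·r)/(1 − r).
- Numbers kept, 450(1 − r): 441, 428 (427.5 rounded up), 405.
- Exact one-sided 5% critical counts: 239, 232, 220. With p exactly 0.50 these tests reject with probability 0.0432, 0.0453 and 0.0455. In all 450 the critical count is 243 and the size 0.049.

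Three settings for q:

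- A: losses are missing lollipop results and 90% of those lost prefer nasal, so q = 0.10.
- B: as A, but only a quarter of the losses reflect intolerance and the rest are neutral, so q = 0.25 × 0.10 + 0.75 × 0.50 = 0.40.
- C: losses are missing nasal results and 90% of those lost prefer the lollipop, so q = 0.90.

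At r = 10% in setting A, for example, p = (0.50 − 0.10 × 0.10)/0.90 = 0.544.

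| Setting | p at 2%, 5%, 10% | Chance of wrongly declaring the lollipop more acceptable |
|---|---|---|
| A | 50.8%, 52.1%, 54.4% | 8.5%, 21%, 54% |
| B | 50.2%, 50.5%, 51.1% | 5.2%, 7.0%, 10.7% |
| C | 49.2%, 47.9%, 45.6% | 2.0%, 0.5%, 0.02% |

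If losses of types A and C are equal in size, the average q is (0.10 + 0.90)/2 = 0.50 and p stays at 50%.

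**Bounds without assuming q.** Suppose 60% of those kept prefer the lollipop. Counting everyone lost against the lollipop, then for it, the share among all 450 lies in:

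- 2% lost: 0.60 × 441/450 = 58.8% to (264.6 + 9)/450 = 60.8%.
- 5% lost: 57.1% to 62.0%.
- 10% lost: 54.0% to 64.0%.

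The two-sided p-values against 50% at the lower ends are 0.0002, 0.003 and 0.09.

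**The case against.** The strongest reply is that section 20.3 was written with Aim 2.2 in mind. Every Aim 2 method in section 20.4 uses PCR results, and section 5.3 ties exclusion to samples that give no result. If no acceptability comparison is specified, the plan cannot be said to drop anyone from it. This is a fair reading, but nothing in the text limits the rule to Aim 2.2. If that was the intent, Aim 2.1 has no population at all, and the same edit is needed.

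Three stronger readings are tempting, and the documents do not support them.

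- *The rule removes the people who tolerated a swab least, so the result is biased towards the lollipop.* Section 5.3 also covers compromised and invalid samples, and nasal results from one laboratory depend on record matching (section 16.5). Section 22.1 reports that a similar method was well tolerated. Missing nasal results would push the other way.
- *The false-positive rate is 54%.* That is the extreme cell of a one-direction setting. Settings B and C are as compatible with the documents, and a 60% preference survives even the worst case at 2% and 5% lost.
- *450 answers are enough, so no sample-size question arises.* An exact one-sided 5% test on 450 independent stated preferences has 82% power at a true 56% and 91% at 57%. If 20% state no preference (assumed), 360 remain and power is 71% and 82%. Answers are also not independent: people may take part more than once (section 7.5) and several children in a family may enrol (section 8.1).

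It also stands that selection begins before the analysis set. Enrollees must be undergoing nasal PCR and decliners are not tracked (section 5.1), and people who refuse a nasal swab by the study team are not enrolled (section 13.3). A new analysis set does not undo this.

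**Conclusion.** The concern holds in this form: a primary objective with a directional hypothesis has no planned analysis, and the only population that could be applied to it is defined by laboratory results irrelevant to preference. Neither statement depends on any assumed rate.

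The effect on the answer cannot be fixed from the documents. Under the stated assumptions the false-positive rate of a nominal 5% test runs from almost zero to 54%, depending on how many people are lost, which swab's result is missing, and how far the loss reflects intolerance. If few results are missing, or the losses balance, the effect is small. The point should be corrected because the change is nearly free, not because a large bias has been shown.

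**What to change.** - In sections 5.3 and 20.3, limit the both-PCR-results rule to Aim 2.2, and bring section 5.2 into line.
- Define the Aim 2.1 set as all enrolled participants who answered the preference question, whatever their PCR results. Report how many enrolled participants gave no answer.
- In sections 20.1 and 20.4, add for Aim 2.1 the share preferring the lollipop among those stating a preference, with a confidence interval and a test against 50% at a stated level and sidedness. The interval and test should allow for repeat participants and siblings, for example by clustering on family.
- Report answers of no preference as their own category. The data collection form is not in the documents, so check that it offers this option.
- Count a refused or incomplete swab against that swab in a sensitivity analysis only. As a primary rule it would impute a preference that nobody stated.
- State as a limitation that people unwilling to have a nasal swab are largely not enrolled.

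The cost is protocol wording and possibly one response option on the form. The downside is that the reported lollipop preference may be slightly less favourable.

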### 20.4 Statistical Methods:

**Aim 1.** Sensitivity, specificity, positive predictive value (PPV) and NPV of the proposed BinaxNOW testing procedure for symptomatic subjects will be calculated and reported along with the corresponding two-sided 95% confidence interval. Formal non-inferiority testing of the BinaxNOW testing procedure with PCR will be conducted with respect to sensitivity and specificity with a non-inferiority margin of  $\delta=5\%$  and a sensitivity/specificity of PCR of 99%.

**Aim 2.** Results obtained from nasal and lollipop swab-based PCR testing will be summarized in tabular format. Concordance between the PCR test results will be evaluated by calculating the Kappa statistic which will be reported along with corresponding two-sided 95% confidence interval. The nonparametric bootstrap technique will be used to construct the confidence interval. A kappa statistic of  $>0.95$  will be considered as sufficient to define lollipop swab test non-inferior to the gold-standard PCR testing of nasal swabs. Furthermore, standard diagnostic test outcomes, i.e., sensitivity, specificity, NPV and PPV will be calculated (using the nasal swab-based

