### 2.3 Significance:

The prevalence of SARS-CoV-2 among school-aged children in the 2021-2022 academic year is unknown. Intense vaccination campaigns will reduce the number of cases, but vaccination uptake varies widely across Wisconsin. Children under the age of 12 years will likely not be eligible for vaccination until the late fall, leaving many children still susceptible to infection during part of the school year. With the large number of children simultaneously returning to school (with many extracurricular activities), and potentially decreased attention to mitigation

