### 5.2 Criteria that define who will be included in the final study sample:

For Aim 1, participants with a negative at-school BinaxNOW test and nasal PCR results who complete both the lollipop PCR and at-home BinaxNOW tests within 72 hours will be included in the final study sample.

Aim 2 will include participants who provide a lollipop swab that is successfully resulted at Exact Sciences or ACL.

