## 13.0 Procedures Involved

13.1 Study Design: This is a quantitative community-based study, conducted in the K-12 setting with school children 4-19 years old, teachers, and staff.

If a participant's initial at-school BinaxNOW test is **positive**, then they will only complete the lollipop swab for PCR testing. They will NOT do the at-home BinaxNOW test virtual visit.

If a participant's initial at-school BinaxNOW test is **negative**, then they will complete both the lollipop swab for PCR testing AND an at-home BinaxNOW test approximately 24 hours later.

If the study team does not have any BinaxNOW tests due to a supply shortage, or if a potential participant is unwilling or unable to complete at-home BinaxNOW testing, the BinaxNOW procedures will be dropped and only the lollipop swab will be collected.

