### 20.2 Sample Size Justification:

For Aim 1, it is anticipated that the majority of initial BinaxNOW tests will be negative. It is hypothesized that the proposed two-day serial testing procedure using BinaxNOW tests in participants with an initial negative test will identify true negatives in >95% of participants. The primary diagnostic outcome measure will be the negative predictive value (NPV). The NPV of BinaxNow is ~91% in symptomatic subjects. For the proposed study, the NPV after the second test (24 hours after the first negative results), is assumed to be substantially higher than 91% since the first test was already negative. In order to detect a true NPV after the second test of at least 95% with 90% power at the one-sided 0.05 significance level, a sample size of N=358 participants with an initial negative test is required. To reach a sample size of N=358 participants with an initial negative test, BinaxNOW kits will be administrated to 400 participants. We intend to continue enrolling until we reach the target sample size of N=358 completing the at-home BinaxNOW test.

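### Aim 1 sensitivity is put to a formal non-inferiority test against 94% with no planned number of PCR-positives, and the plan's own figures point well below that bound

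*Combined protocol and SAP*

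**What the plan says.** Section 20.4 (Aim 1) commits to a test: "Formal non-inferiority testing of the BinaxNOW testing procedure with PCR will be conducted with respect to sensitivity and specificity". The margin is 5% and PCR is taken as 99% sensitive and specific. No test statistic, alpha or sidedness is given. The preceding sentence says that the diagnostic measures "of the proposed BinaxNOW testing procedure for symptomatic subjects will be calculated and reported along with the corresponding two-sided 95% confidence interval".

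The sample size in section 20.2 serves a different measure. NPV is the primary diagnostic outcome, and to detect 95% against 91% "with 90% power at the one-sided 0.05 significance level, a sample size of N=358 participants with an initial negative test is required". The starting value is given as "The NPV of BinaxNow is ~91% in symptomatic subjects".

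The Aim 1 set is restricted. Section 5.2 admits "participants with a negative at-school BinaxNOW test and nasal PCR results who complete both the lollipop PCR and at-home BinaxNOW tests within 72 hours", and section 20.3 agrees: "For Aim 1, we will include all participants who complete the at-home BinaxNOW test within 72 hours (N=358) and have nasal PCR results". Section 13.1 says of those who test positive at school: "They will NOT do the at-home BinaxNOW test virtual visit".

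Section 2.3 adds: "The prevalence of SARS-CoV-2 among school-aged children in the 2021-2022 academic year is unknown". Section 21.1 puts the chance of a positive at-home test below 5%.

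**The concern.** Only PCR-positives count towards sensitivity, and the plan never says how many it expects. Everyone in the Aim 1 set has already tested negative once, so the PCR-positives are the infections that the first test missed. That group is small by design. Section 20.2 ties the procedure to initial negatives, but section 20.4 describes the estimates as applying to symptomatic subjects and does not say that they are conditional.

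The specificity comparison and the NPV test do not show whether missed infections are held to PCR's level. This is the only formal non-inferiority test in Aim 1 that bears on that question. With few PCR-positives, a result of not shown may reflect their number and say little about the test. A result of shown may come from the interval chosen, because none is named. A reader of 20.4 alone could also take the figure for the sensitivity of BinaxNOW testing in all symptomatic people.

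**Working it through.** **Inputs.** Margin 5% and PCR 99% (20.4), so the bound is 99% − 5% = 94%. Single-test NPV 91%, target 95%, one-sided 0.05, 90% power, N=358 (20.2). At-home positives under 5% (21.1). Two readings are mine: a one-sample test against 94%, and a PCR-positive share among at-school negatives of 1 − 0.91 = 9%. Because section 2.3 calls prevalence unknown, higher shares are shown too.

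**The plan's own figure.** An exact binomial test of 91% rejects at 335 or more of 358. Its size is 0.0487 and its power at 95% is 0.909. N=358 is the smallest N that reaches 90%, so it reproduces, for NPV only.

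**Expected PCR-positives.** 358 × 0.09 = 32.2.

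**Fewest PCR-positives that can pass with all detected.**
- Exact: 0.94^n ≤ 0.05 gives n = 49 (60 at 0.025).
- Score: 0.06 / √(0.94 × 0.06 / n) ≥ 1.645 gives n = 43 (61 at 0.025).

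**Chance of passing at one-sided 0.05**, with the number of PCR-positives taken as Binomial(358, share):

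| PCR-positive share | Expected number | All detected: exact / score | True sensitivity 99%: exact / score |
|---|---|---|---|
| 9% | 32 | 0.2% / 3.3% | 0.1% / 2% |
| 12% | 43 | 18% / 52% | 11% / 32% |
| 15% | 54 | 78% / 95% | 44% / 56% |
| 20% | 72 | over 99% / over 99% | 57% / 67% |

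At one-sided 0.025, exact power at 99% is below 0.1%, then 0.3%, 10% and 46%. At 0.05, exact power first reaches 80% at 78 PCR-positives (78/358 = 22%) and stays there from 103 (103/358 = 29%).

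**Dependence on the unnamed method, for 32 of 32 detected.**
- Exact: p = 0.94^32 = 0.138; one-sided 95% lower bound 0.05^(1/32) = 91.1%. Fails.
- Score: lower bound 32 / (32 + 1.645²) = 92.2%. Fails.
- Jeffreys: lower bound 94.2% at 0.05, passes; 92.5% at 0.025, fails.
- Wald: zero estimated variance, passes trivially.

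With exactly 32 PCR-positives, Jeffreys at nominal 0.05 passes only on 32/32. It would therefore pass 13.8% of the time at a true sensitivity of 94%.

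**What the plan's figures imply for sensitivity.** With 9% PCR-positive and specificity 1, NPV = 0.91 / [0.91 + 0.09(1 − Se)]. Setting this to 0.95 gives 1 − Se = 0.91 × (1/0.95 − 1) / 0.09 = 0.532, so Se is about 47%. At-home positives would then be 0.09 × 0.468 = 4.2%, which agrees with the figure in 21.1. That figure means fewer than 0.05 × 358 = 17.9, or 18, positives. A pass needs at least 43 detections (43/358 = 12.0%, score) or 49 (13.7%, exact).

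**Specificity.** With 358 − 32 = 326 PCR-negatives, an exact test at 0.05 allows 12 false positives. Power at a true 99% is above 99.9%.

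**The case against.** The strongest reply is that the 9% is inferred. Section 20.2 gives the 91% for symptomatic subjects in general, with no prevalence or reference standard. A reader might infer that the test would almost surely fail even with perfect detection. That holds for exact and score tests near 9%. The documents do not fix that share, and at 15% perfect detection passes 78% (exact) or 95% (score) of the time at one-sided 0.05. So the stronger statement is not supported. What stands is low power at 99% sensitivity across 9% to 20%.

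Second, NPV is the declared primary diagnostic outcome. Further unpowered tests are common, and the planned two-sided 95% intervals would expose the imprecision. This is fair as far as it goes, and two criteria that can disagree are not in themselves an error. But Aim 1.2 is worded as non-inferiority to PCR, and the NPV test against 91% is not a non-inferiority test.

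Third, 20.4 does not state a one-sample test against 94%. The reading is natural but remains a reading. The missing test and alpha alone would be missing detail; they matter here because 32/32 can pass or fail by method.

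Fourth, the 5% in section 21.1 is a remark about benefits and not a design assumption. It is used only as corroboration.

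A reader might also think that the 50 at-school positives repair the denominator. Counted as detected, they would give 32 + 50 = 82 PCR-positives, enough to pass with perfect detection. Sections 5.2 and 13.1 keep them out of the Aim 1 set.

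**Conclusion.** The concern holds in this form: the plan makes a formal sensitivity claim that its design is very unlikely to support, on an estimate it does not label as conditional. At 9% PCR-positive, about 32 PCR-positives stand against the 43 or 49 needed with perfect detection. At 12% to 20%, the test is underpowered rather than unattainable (exact power 11% to 57% at true sensitivity 99%). The plan's own NPV goal implies about 47% conditional sensitivity, about half the 94% bound, so the trial could succeed on its primary measure and fail here.

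The numbers rest on the 94% reading, on 91% NPV meaning 9% PCR-positive against nasal PCR and, for the 47%, on perfect specificity. The conditional nature of the estimate and the absence of sizing for sensitivity need none of these. A reader might infer that the whole of Aim 1 is undermined. It is not: the NPV sample size reproduces, and the specificity test has ample power. This should be fixed before analysis.

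**What to change.** In section 20.4:
1. State that Aim 1 sensitivity and specificity are conditional on a negative at-school BinaxNOW.
2. Report that sensitivity descriptively with an exact two-sided 95% interval, and draw no non-inferiority conclusion from it.
3. Name the test and alpha for the specificity non-inferiority test that is kept, for example an exact binomial test against 94% at a stated one-sided level.

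In sections 1.0, 3.1 and 3.2, align the non-inferiority wording so that a passed specificity test alone is not presented as non-inferiority to PCR. Identify the NPV test against 91% as the formal evidence on missed infections. Changing 20.4 alone would leave the objectives resting on specificity.

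The cost is wording in these sections, with no new participants, procedures or data. The trial gives up a formal sensitivity claim, and the descriptive interval will be wide: 15 of 32 detected gives 29% to 65%, and 32 of 32 gives 89% to 100%.

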**Diagnostic Testing for SARS-CoV-2 – Nucleic acid detection:**  
The gold standard for diagnostic testing has been detection of SARS-CoV-2 nucleic acids by a polymerase chain reaction (PCR). The first tests to be developed were performed on a sample obtained from the nasopharynx. Eventually, these PCR assays were modified to be performed on other samples including either nasal mucosal swabs or samples of saliva collected in small receptacles. The transition to the use of other samples has been important since acquiring the nasopharyngeal (NP) sample requires trained personnel and is uncomfortable for the patient. Repeated NP tests are dreaded.  
*Identifying the optimum sampling technique for children remains a challenge.*

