## PROTOCOL TITLE: SAFE AND HEALTHY SCHOOLS

testing as gold standard), and reported along with the corresponding two-sided 95% confidence intervals. Formal non-inferiority testing of the lollipop swab test with PCR will be conducted with respect to sensitivity and specificity with a non-inferiority margin of  $\delta=5\%$  and a sensitivity/specificity of PCR of 99%. Statistical analyses will be conducted using SAS software (SAS Institute, Cary NC), version 9.4 or greater.

20.6 Handling of Missing Data: The primary analysis for evaluating the diagnostic utility of the BinaxNOW testing procedure will be based on the complete case principle. Since the analyses of this study won't involve any formal multivariate or longitudinal statistical modeling, no imputation-based analyses will be conducted.

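### Section 20.4 uses nasal PCR both as the error-free reference and as a comparator fixed at 99%, so the 94% sensitivity bar does not measure non-inferiority to PCR within 5 points

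*Combined protocol and SAP*

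**What the plan says.** For Aim 1, section 20.4 reports sensitivity, specificity, PPV and NPV of the serial BinaxNOW procedure. It then adds formal non-inferiority tests on sensitivity and specificity with a 5-point margin "and a sensitivity/specificity of PCR of 99" percent. Aim 1 names no reference. Nasal PCR is the only candidate: section 20.3 restricts the analysis to those who complete the home test in time "and have nasal PCR results", section 5.3 excludes anyone without a nasal PCR result, and section 2.3 calls PCR the gold standard.

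For Aim 2 the reference is explicit. The lollipop is scored with nasal swab-based "testing as gold standard), and reported along with the corresponding two-sided 95% confidence intervals". The next sentence reads "Formal non-inferiority testing of the lollipop swab test with PCR will be conducted with respect to sensitivity and specificity", with the same margin and the same 99%.

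The only sample-size calculation is for NPV, in section 20.2: "The NPV of BinaxNow is ~91% in symptomatic subjects", and the trial is sized to detect a "true NPV after the second test of at least 95% with 90% power at the one-sided 0.05 significance level", giving N=358. The sensitivity and specificity tests have no stated hypotheses, significance level, prevalence, expected number of PCR-positives or power.

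**The concern.** A test scored against itself has sensitivity and specificity of 100%. Nasal PCR cannot be that reference and also a comparator with 99% of each. The documents do not say how the two combine. The natural arithmetic, 99 minus 5, gives a bar of 94% for measured agreement with nasal PCR, and that is not a difference from PCR's own accuracy.

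The consequence depends on what the 99% means. If it describes real PCR error, some PCR-positives are false, and a test that is always right is charged with missing them. If it is only a number used to set the bar, that bias goes away, but so does the meaning of the margin. Non-inferiority is the hypothesis of both aims (sections 3.1 and 3.2). As written, a failed sensitivity test could reflect assumed PCR error or too few positives, and a pass could not be reported as lying within the stated margin of PCR.

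**Working it through.** **The plan's own figure.** A one-sample exact binomial test of NPV 91% against 95%, one-sided 0.05, rejects at 335 or more true negatives out of 358 (size 0.0487, power 0.909). 358 is the smallest N that reaches 90% power, so the stated N is reproduced. It supports the NPV test only.

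**Inputs.** From section 20.4: margin 5 points and PCR 99%/99%, so the bar is 0.99 − 0.05 = 0.94. From sections 4.2 and 20.2: 358 antigen-negative completers (400 given kits) and 50 antigen-positives. Assumed, because the documents give no prevalence:
- 5% to 9% infected among first-test negatives. The 9% comes from 1 − 0.91; the 5% is suggested by section 21.1, which puts home-test positivity below 5%.
- 90-100% infected among the 50 antigen-positives.
- Exact lower confidence bounds at one-sided 0.05.

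**Reading A: PCR truly is 99%/99%.** Take an index test that is always right. With prevalence p, its apparent sensitivity against PCR equals the PPV of PCR:

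0.99p / (0.99p + 0.01(1 − p))

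- p = 0.05: 0.0495 / (0.0495 + 0.0095) = 0.839
- p = 0.09: 0.0891 / (0.0891 + 0.0091) = 0.907
- p = 0.15: 0.1485 / (0.1485 + 0.0085) = 0.946
- p = 0.17: 0.1683 / (0.1683 + 0.0083) = 0.953
- p = 0.19: 0.1881 / (0.1881 + 0.0081) = 0.959

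Setting the expression to 0.94 gives p = 0.0094 / (0.0594 + 0.0094) = 0.137. Below 13.7% infected, a perfect test is expected to fall short of the bar.

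*Aim 1, N=358.* About 3 PCR-positives are false (358 × 0.01 × 0.95 = 3.4; 358 × 0.01 × 0.91 = 3.3), out of about 21 and 35 PCR-positives in all. A perfect test passes with probability 0.0001 or less.

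*Aim 2.* Infected fractions of 15%, 17% and 19% of 450 people are about 68, 77 and 86. Using these as the numbers of PCR-positives, the exact rule requires 68/68, 77/77 and at least 85/86 concordant. A perfect lollipop passes with probability 0.023, 0.025 and 0.125. Averaging over the random number of PCR-positives, across scenarios with 14-20% infected, gives 0.026-0.133.

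*Specificity.* Apparent specificity equals the NPV of PCR: 0.9995 at 5%, 0.9990 at 9% and about 0.998 at 15-19%. It passes with probability about 1 in both aims.

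**Reading B: 99% only sets the bar and PCR is treated as error-free.** A perfect test then agrees completely. With n of n concordant, the one-sided 95% lower bound is 0.05^(1/n): 0.9395 at n=48 and 0.9407 at n=49, so at least 49 PCR-positives are needed (60 at one-sided 0.025).

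- Aim 1 expects 358 × 0.05 = 18 to 358 × 0.09 = 32. Complete agreement gives bounds of only 0.847 (18/18) and 0.911 (32/32).
- Aim 2 expects about 63 (358 × 0.05 + 45) to 86 (400 × 0.09 + 50). A perfect lollipop passes with probability 0.98-1.00 (0.68-1.00 at one-sided 0.025).

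**The case against.** A reader might infer that even a perfect antigen or lollipop test would be expected to fail non-inferiority outright. The documents do not support that, for four reasons.

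- Half of what is tested is specificity, which passes almost surely.
- In Aim 2 the expected sensitivity of a perfect lollipop under Reading A lies above 94%. The low pass probability there comes from imprecision, not from an expected value under the bar.
- Section 20.4 nowhere says that PCR error will be modelled. A fixed benchmark is a fair plain reading, and under it a perfect lollipop would most likely pass.
- Reading A takes a round 99% as literal specificity. With sensitivity kept at 99%, a specificity of 99.5% gives 0.0495/0.05425 = 91.2% at 5% infected and 0.0891/0.09365 = 95.1% at 9%. At 99.9% the figures are 98.1% and 99.0%.

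It is also fair that Aim 1 sensitivity fails under either reading, because PCR-positives are too few, so the 99% is not the sole cause. Aim 2 further admits Lollipop Only participants of unknown prevalence, so its 15-19% is soft.

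All of this limits the size of the problem. The inconsistency remains. Under the benchmark reading, 94% is an agreement threshold and still says nothing about a 5-point difference from PCR. The lollipop sensitivity result turns on which reading applies, and the plan does not say.

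**Conclusion.** The point holds for the sensitivity tests. Nasal PCR is both a 100% reference and a 99% comparator, and clearing 94% would not establish non-inferiority to PCR within 5 points. Under the plan's own 99%/99%, a perfect test has apparent sensitivity of 83.9-90.7% in Aim 1. In Aim 2 it has 94.6-95.9%, with about a 2-13% chance of passing. With 99% as a mere benchmark, a perfect lollipop passes with probability 0.98-1.00 and Aim 1 still cannot succeed.

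These sizes rest on the assumed prevalences, the assumed infection rate among antigen-positives, the choice of one-sided 0.05 and the exact bound; none of these is stated for these tests. The inconsistency itself rests on no assumption beyond nasal PCR being the Aim 1 reference. The Aim 1 primary measure, NPV against 91%, does not use the 99% and is unaffected.

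**What to change.** In section 20.4:

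1. Remove the assumed 99% from both aims.
2. Name nasal PCR as the Aim 1 reference.
3. Report positive and negative percent agreement with nasal PCR, with confidence intervals, and word the results as agreement.
4. If 94% is kept, state it as a fixed agreement goal and not as non-inferiority to PCR.
5. Make no formal sensitivity non-inferiority claim for Aim 1.

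A composite reference that counts either PCR swab as positive should not be used for Aim 1. Nasal PCR sits inside it and antigen does not. If both swabs are 99%/99% with independent errors, the composite is positive in 0.9999 of infected and 0.0199 of uninfected people. A perfect antigen test then trails nasal PCR by (0.0590 − 0.0500)/0.0689 = 13.1 points at 5% infected and (0.0982 − 0.0900)/0.1081 = 7.6 points at 9%.

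For Aim 2, a paired comparison of lollipop and nasal positivity that treats the two swabs symmetrically may be added as supportive. If an either-positive composite is used there, say that it counts false positives as infections and cannot assess specificity.

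The cost is SAP wording and a small analysis of data already being collected. The trial gives up a formal sensitivity non-inferiority claim.
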